5.1 Study Measurements

5.1.1 Safety

All adverse events will be recorded and evaluated for severity.

5.1.2 Feasibility

Before the procedure the density (number of hairs per square centimeter) and thickness (mm) of the hair will be measured and compared to the same measurements after the procedure at 3 and 6 months.

5.2 Study Visit and Procedures

5.2.1 Visits

There will be between 7 and 8 study visits for each subject (screening and pre-surgery 1 may be combined). Each office visit will take approximately 0.5 hour. The procedure visit will be conducted at the same center on an outpatient basis.

5.2.2 Recruitment

Subjects will be recruited via; 1) email utilizing a list of patients that have given their prior consent to be contacted in this manner 2) at the PI's office when they come in for their regularly scheduled appointments 3) referrals from healthcare professionals within the community or 4) via IRB approved flyers. Subjects recruited via email or flyer will be requested to call in for more information. Designated office staff will screen subjects in the office or on the phone to evaluate eligibility.

5.2.3 Informed Consent & HIPAA

The Consenting Process will only be done by the PIs or other qualified consent designees. The PI or consent designee will conduct a complete interview for each potential Subject. The PI and authorized consent designees have clinical experience, have completed either CITI and/or NIH training "Protecting Human Research Participants", and have individual expertise and training detailed in their respective curriculum vitae or resumes.

The PIs and authorized consent designees will describe the project, its goals, expectations of the study, description of inclusion/exclusion criteria for the participants, the liposuction surgery, fat processing to obtain cells, scalp injections, events at the study visits, questionnaires to be used, that their participation has potential (but not guaranteed) direct medical benefit to them, and that the study may provide new knowledge relevant to potential use of cells or tissue therapies in the future. Each subject must be informed that participation in the study is voluntary and that he/she may withdraw from the study at any time and that withdrawal of consent will not affect his/her subsequent medical treatment or relationship with the treating physician.

The PI or consent designee will review the elements of HIPAA and Protected Health Information (PHI) with each participant and each participant will be asked if s/he understands HIPAA authorization and PHI. Each participant will be asked to voluntarily sign a study Informed Consent Form and HIPAA Authorization Form before any study-related procedure is performed. The subject will sign the consent form if willing to proceed or decline any further participation if unwilling. Informed Consent Forms must be dated and signed by the PI or consent designee and participant or the participant's legal representative and the original signed consent form kept by the Investigator in the study patient's file. "Legal representative" means an individual or judicial or other body authorized under applicable law to consent on behalf of a

prospective participant to the participant's participation in the procedure(s) involved in the research. A copy of the signed consent documents will be provided to each subject.

5.2.4 Enrollment

The subject will be assigned an anonymous, unique identifier called the Subject ID unrelated to the subject's name from a list of possible ID's. The subject's name and corresponding identifier will be recorded in a study look up document, which shall be kept at the study site.

The subject ID of excluded subjects will not be re-assigned. Information describing the reason(s) for exclusion will be documented on the Inclusion/Exclusion CRF.

5.2.5 Study Timeline

Initial Contact to Informed Consent – The timing from the initial contact and obtaining consent at the Pre-surgery #1 is expected to range from the same day up to two (2) weeks depending on participant and physician availability. Potential Participants will have the option of taking additional time to review the documents, but it is expected that the dates for surgery will be set within two to four weeks depending on scheduling. A potential Participant will need to have all documents signed and in place prior to surgery and if they choose to participate in the project the study documents will be included in the package.

5.2.6 Methods

1. Liposuction will be performed at the clinical site according to standard clinical practice.
2. The surgery and scalp injection will be conducted on the same day within 1.5 hours from collection of adipose to injection in the scalp.
3. At the conclusion of the fat harvest procedures, support garments and dressings are worn by the Subject to control swelling and promote healing.
4. Processing of the fat will be done immediately after harvest using a sterile single use disposable (GID SVF-2) and according to the instructions for use with the device. The GID SVF-2 is an investigational device and will be labeled as such.
5. **Injection of Cells into Scalp**
The scalp will be cleansed with 70% alcohol, and 1% lidocaine will be injected as a regional nerve block. All of the SVF will be injected under the scalp at the superficial subcutaneous plane in a 2 x 2 cm area.
6. **Hair Measurements**

Refer to the Hair Measurement CRF for location of 2 x 2 cm area. Hair measurement will be made using a computerized handheld USB camera at baseline and 3 and 6 months after treatment.

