Fukuoka et al reported on 2 groups of patients with alopecia⁹. One group had 11 men and 11 women that were treated with 6 injections spaced every 3 to 5 weeks of adipose-derived SVF and monitored for up to 7 months. They found a significant increase in hair growth and reported no adverse events or safety issues. In the second group 10 patients (8 men and 2 women) were treated on one side with adipose-derived SVF and the other with placebo (saline). Patients were blinded to the treatment. This group also received 6 injections similar to the other group. The treatment group had significantly more hair growth than the control side.

A hair regeneration procedure that is less invasive than surgical hair transplantation, entails less risk than current surgical treatments, and is less time consuming would benefit men and women with alopecia.

2 Study Objectives

The general objective of this study is to conduct a safety and feasibility study of a single injection of autologous adipose-derived SVF for the treatment of alopecia.

3 Study Design

This is a prospective, non-randomized, non-blinded, interventional, consecutive series, multiple site study to determine initial safety and feasibility of a single injection of autologous adipose-derived SVF for the treatment of alopecia.

4 Study Population

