4.2 Study Site Selection

A maximum of three sites will participate in clinical data collection. The subjects will be divided equally among the sites as much as possible.

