5.2.9 Case Report Forms

All clinical data obtained will be recorded on source documents (i.e. study chart) and information required by the protocol will be copied onto the case report forms (CRFs). CRFs for each subject enrolled in the study will be stored in a binder. The appropriate CRFs will be completed and signed by the PI. All CRFs will be completed in a legible manner in ink. Any corrections required will be made by drawing a single line through the incorrect entry, entering the correct information, and initialing and dating the change.

During the study, the quality of the data will be assured by the presence of site personnel who will check the CRFs against the site's source documents for completeness and to ensure that data is collected in adherence to the protocol. Evident recording errors will be rectified by the clinical site.

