7.2 Statistical Methods

Hair density and thickness will be compared pre and post treatment. The data gathered will be used to establish a baseline difference for future studies.

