7.3 Procedure for Accounting for Missing, Unused or Spurious Data

Any missing, unused, or spurious data will be noted in the study records. Data may be removed if it does not meet quality criteria.

8 Ethical and Regulatory Considerations

This study must be carried out in compliance with the protocol and in accordance with the site's standard operating procedures. These are designed to ensure adherence to Good Clinical Practice (GCP) guidelines, as described in:

- Code of Federal Regulations, Title 21, Parts 50, 56, and 812.
- World Medical Association Declaration of Helsinki: Ethical Principles for Medical Research Involving Human Subjects 2013.
- ICH E6 Good Clinical Practice April 1996

The investigator agrees, when signing the protocol, to adhere to the instructions and procedures described in it and thereby to adhere to the principles of GCP to which it conforms.

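### Nothing in the plan hides the visit from whoever produces the hair readings, so operator-dependent readings could bias the uncontrolled pre/post change that Section 7.2 carries forward

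*Combined protocol and SAP*

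**What the plan says.** The Summary and Section 3 declare the design openly: "This is a prospective, non-randomized, non-blinded, interventional, consecutive series, multiple site study".

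Section 5.1.2 defines feasibility as a within-subject comparison. Density before the procedure is set against later density, and likewise "thickness (mm) of the hair will be measured and compared to the same measurements after the procedure at 3 and 6 months".

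The measurement method is in Section 5.2.6, item 6: "Hair measurement will be made using a computerized handheld USB camera at baseline and 3 and 6 months after treatment". The same item sends the reader to a form for the location only: "Refer to the Hair Measurement CRF for location of 2 x 2 cm area". That form is not among the documents.

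On recording, Section 5.2.9 says "The appropriate CRFs will be completed and signed by the PI". It also has data entered in source documents first, then copied to the CRFs, with site personnel checking one against the other.

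On removal of data, Section 7.3 says "Data may be removed if it does not meet quality criteria". Section 5.2.10 covers the same step more tightly: exclusion criteria are to be fixed in advance, analysable subjects chosen before database lock, and exclusions and outliers explained in the study report.

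On use of the result, Section 7.2 says "The data gathered will be used to establish a baseline difference for future studies".

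**The concern.** With one arm, any reading error that tracks the visit goes straight into the pre/post change, because no comparison group shares it. A person who judges which hairs to count, or where to measure thickness, and who knows whether the image is from baseline or Month 6, may read the two differently without meaning to. The same knowledge can affect which images are judged unusable.

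The plan sets no success criterion and names no hypothesis test, so the harm is not a false claim of efficacy from a formal test. What is at stake is the value that Section 7.2 hands on: a later study planned on a biased difference would be too small.

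**Working it through.** **Step 1. Does any section hide the visit at reading?**

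| Section | What it controls | Hides the visit? |
|---|---|---|
| Summary, 3 | Declares the study non-blinded | No |
| 5.2.6 item 6 | Camera and time points | No; silent on reader, saved images, software and reading order |
| 5.2.8 | General commitment to accurate and reliable data | No |
| 5.2.9 | Source first, then CRF, with a check between them | No; finds copying errors, not a biased reading |
| 5.2.10 | Criteria fixed in advance, subjects selected before lock, exclusions reported | No; lock comes after readings are entered |
| 7.3 | Allows removal on quality grounds | No |
| 8.5 | Sponsor monitoring | No |

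In 5.2.6 the word for computer control describes the camera. It does not say that counting is automatic, so operator input is neither established nor ruled out.

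**Step 2. Illustration of the carry-forward.** The plan has no figure to reproduce: N = 8 comes without an SD, an expected difference or a power. All of the following is assumed. A later two-arm trial takes the whole pilot change as its between-arm difference and is sized for 80% power, two-sided 5%. A share b of that change is reader bias, and the rest is real.

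True power = Φ[(1 − b)(1.960 + 0.842) − 1.960]

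- b = 0: Φ(2.802 − 1.960) = Φ(0.842) = 80%
- b = 0.10: Φ(2.522 − 1.960) = Φ(0.562) = 71%
- b = 0.20: Φ(2.242 − 1.960) = Φ(0.282) = 61%

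An exact two-sample t calculation with a planned standardised difference of 0.5 and 64 per arm gives 0.612 at b = 0.20, in agreement.

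**Step 3. Illustration of selective removal.** Assume 8 independent normal changes and that the least favourable one is dropped. The mean of the remaining 7 exceeds the mean of all 8 by (mean of 8 − minimum)/7. The expected minimum of 8 standard normals is −1.424, so the average rise is 1.424/7 = 0.20 SD. This is an average and not a ceiling: by simulation it is exceeded in about 45% of samples, and the 95th percentile is about 0.33 SD.

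**Step 4. Workload.** 8 subjects × 3 time points = 24 images, more if several are taken per visit.

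**The case against.** The strongest reply is that this is an eight-subject pilot, openly non-blinded, which lists safety first and tests no hypothesis, and that the concern depends on operator input that the document does not establish. Most of that stands. The open design is a legitimate choice and is not the complaint; masked reading of stored images is compatible with unblinded treatment. The dependence on operator input is real, and the Hair Measurement CRF may settle it, although 5.2.6 cites that form only for location.

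Several stronger readings are tempting and are not supported:

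- *That the investigator counts the hairs.* Section 5.2.9 makes the investigator complete and sign the forms, but values reach them by copying from source documents. That shows who records, not who reads.
- *That data can be dropped at will.* Section 7.3 alone might suggest it. Section 5.2.10 requires criteria fixed in advance and reported exclusions, which makes the worst case in Step 3 less likely. The criteria are not listed, however, and the visit is not hidden when they are applied.
- *That the bias must favour treatment.* That is a plausible direction, but nothing in the document supports it.
- *That all change not due to SVF is reader bias.* Natural change, relocation of the square and image capture also enter the pre/post difference, and masked reading does not touch them.

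It is also fair to object that the planning use in Step 2 is invented. Section 7.2 does not say how the difference will be used.

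**Conclusion.** The concern holds in conditional form. The plan does not hide the visit from whoever produces density and thickness. If an operator has any input, the uncontrolled change carried forward by Section 7.2 is open to reader bias. If software gives both values with no operator input, it is not.

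The size is unknown. Power of about 61% instead of 80% rests on an assumed 20% reader share and an assumed planning use; with no reader bias the loss is nil. The 0.20 SD average shift from one removal assumes normal changes and the worst choice of subject.

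This is an inexpensive improvement that should be made before baseline images are taken. It is not a flaw that invalidates the pilot.

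**What to change.** Add to Section 5.2.6, item 6:

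> Images are saved at baseline, 3 and 6 months and checked for usable quality at the visit, before injection at baseline. Existing personnel other than the measurer, or a script, give the files a random code showing no date or visit. Where an operator has any input into density or thickness, the measurer reads all of a subject's images in random order with visit hidden, after the Month 6 image or exit, and any removal of an image on quality grounds (5.2.10, 7.3) is decided before visit is revealed. If software gives both values with no operator input, this is stated and masked reading is not needed.

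Where existing staffing allows, the measurer should not be the person who took the images. This may be hard to arrange: "A maximum of three sites will participate in clinical data collection", and with three sites there would be about 3 subjects at each (8/3 ≈ 2.7).

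Cost: at least 24 images to save and code, and a short usability check at each visit, with the same camera, visits and personnel. The baseline check matters because that image cannot be retaken after injection, and losing one subject loses 1/8 = 12.5% of the data. Month 3 values become available later, but no decision in the document depends on them.

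Limits: masking reduces reader bias without guaranteeing its removal, since change may be visible in the image or the measurer may recall it. It does nothing about image capture, relocation of the area or natural change.

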5.2.7 Adverse Events

Although the actual study poses no threat or risk above that for the liposuction/fat harvesting procedure and scalp injection, any Adverse Event or Serious Adverse Event experienced by a participant involved in the study, whether or not due to the study, will be reviewed and evaluated for appropriate follow-up actions (see Adverse Events, Side Effects and Other Risks, Section 6). An Adverse Event Form or Serious Adverse Event Form will be filled out if such an event occurs and communicated directly to the Sponsor within 3 days.

5.2.8 Data Collection

The investigator will train his/her study personnel regarding the study protocol. This training will take place prior to enrollment of the first subject. The study site shall maintain applicable regulations specific to the conduct of clinical studies. Steps will be taken in the planning and implementation of this study to ensure that the data collected are accurate, consistent, complete and reliable.

During the study, patient data paperwork will be kept using standard patient records criteria, confidentiality and information security procedures that include limited access, Co-PI oversight of records, and secured files. The data will be stored consistent with the clinics Records Retention Policies.

5.2.9 Case Report Forms

All clinical data obtained will be recorded on source documents (i.e. study chart) and information required by the protocol will be copied onto the case report forms (CRFs). CRFs for each subject enrolled in the study will be stored in a binder. The appropriate CRFs will be completed and signed by the PI. All CRFs will be completed in a legible manner in ink. Any corrections required will be made by drawing a single line through the incorrect entry, entering the correct information, and initialing and dating the change.

During the study, the quality of the data will be assured by the presence of site personnel who will check the CRFs against the site's source documents for completeness and to ensure that data is collected in adherence to the protocol. Evident recording errors will be rectified by the clinical site.

5.2.10 Data Management and Quality Control

A clinical study database will be generated by The GID Group, Inc. and/or by their representative to record all clinical data from the CRFs. Deviations, discrepancies and missing data will be investigated. After all protocol deviations and/or discrepancies are resolved and all corrections and clarifications are made to the database, the database is declared complete, accurate and locked.

Any missing, unused, or spurious data will be noted in the study report. Data may be disqualified if it meets the pre-determined exclusion criteria. Selection of the acceptable subjects for data analyses will be established prior to the database lock. A discussion of any outliers and reasons for excluding subjects or data will be documented and summarized in a study report.

5.3 Subject Exit and Study Completion Procedures

5.3.1 Subject Exit Status

Subjects shall exit the study with a status as one of the following:

1. Completing
One who completes all required study visits.
2. Non-completing
 - a. One who exits the trial by his or her own volition or at the discretion of the PI.
Any subject may decide to voluntarily withdraw from the trial at any time without prejudice.
 - b. Non-completions are to be characterized as:
 - i. One who does not complete all the study visits.
 - b. The particular reason for non-completion should be documented on the CRF.
3. Termination
Subjects may be terminated from the study at the discretion of the PI only for reasons related to the study examinations that would jeopardize the subject's health and/or welfare if they were to continue in the study.

5.3.2 Completed Study

The trial is completed when the planned enrollment has been completed, and the enrolled subjects exit the study.

6 Side Effects, Adverse Events and Other Risks

The Study adds no expected risks or the need for additional safety precautions for the Subject beyond what they would have for the standard Liposuction surgery and scalp injection. These are detailed in the INFORMED CONSENT - LIPOSUCTION (Suction-Assisted Lumpectomy Surgery) and the CONSENT FOR SCALP INJECTION PROCEDURE.

Throughout the course of the proposed study, all efforts will be made to remain alert to possible adverse events or untoward findings. If an adverse event occurs, the first concern will be the safety of the subject. Appropriate medical intervention will be made. Any adverse events observed by the investigator or reported by the subjects, regardless of severity and whether or not ascribed to the research procedures, will be recorded in the appropriate section of the subject's CRF. Any subjects who are terminated from the study due to adverse events will be followed until their medical outcome is determined.

7 Statistical Analysis

7.1 Sample Size

This is a pilot study with a sample size of N=8 participants.

7.2 Statistical Methods

Hair density and thickness will be compared pre and post treatment. The data gathered will be used to establish a baseline difference for future studies.

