4. Individuals with diminished decision-making capacity will not be included in this research study.
5. Current use of anti-inflammatory or anticoagulation medications that affect bleeding or are for bleeding disorders. These include: Plavix, Warfarin (Coumadin, Jantoven, Marfarin).
6. Use of concomitant treatments, including topical medications, oral medications, meso-therapy, non-ablative fractional laser treatment, low-level laser therapy, interfollicular PRP injection and hair transplantation within the preceding 6 months.
7. All smokers and other tobacco users.

| | |
|------------------------------------|---|
| Subject | Subjects will be recruited from the practice of the Principal Investigator (PI) at each site and/or other colleagues and healthcare professionals in the community. Recruitment will be prospective for this study. Subjects will be recruited via; 1) email utilizing a list of patients that have given their prior consent to be contacted in this manner 2) at the PI's office when they come in for their regularly scheduled appointments or 3) referrals from healthcare professionals within the community or 4) via IRB approved flyers. |
| Investigational Sites | Up to 3 sites |
| Estimated Total Sample Size | Eight (8) subjects will be recruited to participate in the study. This study is a small pilot safety and feasibility study not requiring sample size. |
| Plan for Data Analysis: | Adverse events will be recorded. Hair density (hairs per square centimeter) and hair thickness will be compared pre and post treatment. |

Table of Contents

| | | |
|--------|---|----|
| 1 | Introduction | 6 |
| 2 | Study Objectives | 6 |
| 3 | Study Design..... | 6 |
| 4 | Study Population..... | 7 |
| 4.1 | Subjects..... | 7 |
| 4.1.1 | Inclusion Criteria | 7 |
| 4.1.2 | Exclusion Criteria..... | 7 |
| 4.2 | Study Site Selection..... | 7 |
| 4.3 | Concomitant Medications..... | 7 |
| 5 | Study Visits and Methods | 9 |
| 5.1 | Study Measurements..... | 9 |
| 5.1.1 | Safety | 9 |
| 5.1.2 | Feasibility | 9 |
| 5.2 | Study Visit and Procedures | 9 |
| 5.2.1 | Visits..... | 9 |
| 5.2.2 | Recruitment | 10 |
| 5.2.3 | Informed Consent & HIPAA..... | 10 |
| 5.2.4 | Enrollment..... | 11 |
| 5.2.5 | Study Timeline..... | 11 |
| 5.2.6 | Methods..... | 11 |
| 5.2.7 | Adverse Events..... | 12 |
| 5.2.8 | Data Collection..... | 12 |
| 5.2.9 | Case Report Forms..... | 12 |
| 5.2.10 | Data Management and Quality Control..... | 12 |

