4.1 Subjects

A total number of eight (8) subjects from a single population, i.e., patients who have been diagnosed with androgenetic alopecia, will be recruited.

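### Does section 7.2 pass an uncontrolled pre-post change in 8 subjects to future studies as if it were an SVF effect?

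*Combined protocol and SAP*

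**What the plan says.** The statistical methods section (7.2) has two sentences. One says that density and thickness will be compared before and after treatment. The other is "The data gathered will be used to establish a baseline difference for future studies". It does not define the term baseline difference, and it names no summary statistic, interval or visit.

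The rest of the protocol fixes the design:

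- Section 4.1: "A total number of eight (8) subjects from a single population". There is no second group.
- Section 5.1.2: baseline density and thickness are "compared to the same measurements after the procedure at 3 and 6 months", so each subject's own baseline is the only comparator described.
- Section 5.2.6, item 5: "All of the SVF will be injected under the scalp at the superficial subcutaneous plane in a 2 x 2 cm area".
- Section 5.2.6, item 6: "Refer to the Hair Measurement CRF for location of 2 x 2 cm area", and "Hair measurement will be made using a computerized handheld USB camera at baseline and 3 and 6 months after treatment". That form is not among the documents, so a reference area listed only there cannot be excluded. The protocol itself describes none.
- Summary and section 3: "This is a prospective, non-randomized, non-blinded, interventional, consecutive series, multiple site study to determine initial safety and feasibility".
- Summary, sample size row: "This study is a small pilot safety and feasibility study not requiring sample size".

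**The concern.** A single-group pre-post change is not a treatment effect. Over 3 to 6 months hair density may shift by itself, camera readings may drift, the injection may act apart from the cells, and readers know that the area was treated. The protocol describes nothing that separates these from SVF, and neither their direction nor their size is known.

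The sentence in section 7.2 gives the figure a life beyond this study. The introduction describes earlier SVF work as having found the treatment safe and effective, so a later reader could take an unlabelled difference for an SVF effect and plan a controlled trial on it. If part of the change were not SVF, that trial would be too small. If drift had hidden part of the effect, it would be larger than necessary. The introduction also cites a split-scalp study with a saline side, so the authors knew of a controlled layout.

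**Working it through.** **What follows from the documents.** The only numerical input is N = 8 (section 7.1). The protocol gives no SD, effect size, significance level or power, so there is no sample size calculation to reproduce. Results are in units of the SD of the change, taking changes as roughly normal.

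- Half-width of the 95% CI for the mean change: t(0.975, 7)/√8 = 2.365/2.828 = 0.84 SD. With 7 or 6 evaluable subjects it is 0.92 or 1.05 SD.
- 95% limits for the true SD, as multiples of the estimate: √(7/χ²) at the upper and lower 2.5% points of χ² on 7 df, giving 0.66 and 2.04.

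So the figure is imprecise, as expected of a pilot of this size. The report can show this directly from the data.

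**What would happen if the change were misread (assumed drift).** Let the non-SVF part of the mean change be d SD. The ordinary 95% CI covers the SVF effect with probability P(|T| < 2.365), where T is noncentral t with 7 df and noncentrality d√8.

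| Assumed d | Coverage of the SVF effect |
|---|---|
| 0 | 95% |
| 0.25 | 91% |
| 0.5 | 77% |
| 1.0 | 32% |

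Suppose a later two-arm trial were sized on an observed change of 1.0 SD (two-sided 5%, 80% power, normal approximation). Then n per arm = 2(1.960 + 0.842)²/1.0² = 15.7, so 16. Power at a true effect δ is Φ(δ√(16/2) − 1.960):

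- δ = 1.0: Φ(0.868) = 81%
- δ = 0.75: Φ(0.161) = 56%
- δ = 0.5: Φ(−0.546) = 29%

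The loss is real under these assumptions. But the protocol supplies neither the drift nor the sizing step. The harm needs a future planner to read a change openly described as uncontrolled as if it were controlled.

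**Would an untreated area help?** Let ρ be the correlation between the changes in the two areas, with equal SDs, and let m be the number of subjects who have a control area. The treated-minus-untreated contrast has SD √(2(1 − ρ)). Inclusion criterion 3 (section 4.1.1) requires only one 2 x 2 cm spot, so m may be below 8. Take m = 6 as an example:

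- The contrast half-width is 1.24, 1.05 or 0.81 SD at ρ = 0.3, 0.5 or 0.7, against 0.84 for the raw change in all 8.
- Mean squared error at d = 0.25 and ρ = 0.3, with all drift shared by both areas: contrast 2(0.7)/6 = 0.233; raw 0.25² + 1/8 = 0.188. The contrast is worse.
- With all drift shared, the contrast has the smaller error only when d exceeds √(2(1 − ρ)/6 − 1/8), which is 0.33 at ρ = 0.3 and 0.20 at ρ = 0.5. At ρ = 0.7 it is never worse.

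Whether the control area helps therefore depends on d, ρ, m and how much drift is shared. The documents give none of these.

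**The case for a change.** The best case for a change is that the forward use is the protocol's own statement, not a reader's guess. The term is undefined, the visit that supplies it (3 or 6 months) is not named, and no caveat appears anywhere. A short sentence with n, mean, SD, CI and a limit on use would need no new data and could prevent a foreseeable misreading.

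The description of the gap stands: section 7.2 is thin and its wording loose. The need for an amendment does not. The same measurements would be taken at the same visits, and the same mean, SD and interval can be computed at both 3 and 6 months with or without the sentence. An analyst writing up 8 paired changes would report them that way. The limits of the design are visible to any later reader, because the protocol states that the study is non-randomized, non-blinded and a small pilot. A statement that the change is not an SVF effect would also go too far: the change may contain one, and the design simply cannot isolate it.

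The case for a control area is weaker as a required change. When drift is large and shared, the contrast is better. Against that, it adds a second relocation error, is open to unblinded reading, could be shrunk by spread of SVF, does not control for needle, anaesthetic or fluid effects, and would rest on subjects selected for wider thinning.

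**Conclusion.** The observation is accurate but calls for no change. Section 7.2 leaves a term undefined and omits a caveat, and a competent report supplies both without altering the data or the estimates. An uncontrolled pre-post comparison is a fair choice for a safety and feasibility pilot, and the protocol does not present the result as an SVF effect.

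Only the precision figures rest on the documents: a half-width of 0.84 SD and an SD range of 0.66 to 2.04 times the estimate at N = 8, assuming roughly normal changes. The coverage, power and contrast figures depend on assumed drift, correlation and later use, so they illustrate a possible misuse and do not measure a defect in this plan. An untreated area is a design option with gains and losses, not a correction.
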